Adult vaccination with the 23-valent polysaccharide (PPV23) officially started in 2004, and with PCV13 in 2016 for some cohorts. Most adult pneumococcal vaccination occurs during annual influenza vaccination campaigns. Pneumococcal vaccination for adults in the Madrid region changed as of January 2018. An overview of pneumococcal adult vaccination is described in Table 1.

Note that for persons ≥ 60 years with past PPV23 administration, only those with underlying disease or at high risk will be given PCV13, and others without risk factors will not receive another pneumococcal vaccination (Table 1). Thus, in the ≥ 60 years age group, the population with PCV13 will be enriched for those with risk factors, and this will need to be accounted for in the analysis as a source of confounding (ie, confounding by indication).

Current PCV13 and PPV23 average uptake in Madrid Region as of March 2019 is described in Table 2, with a peak for PCV13 in people of 63 years old (see Table 2). People of over 60 years in the whole of Madrid region are 1,511,750 as of January 2018 (Instituto Nacional de Estadística, INE, www.ine.es).

The Regional Health System operates a database known as "Sistema de Información en Salud Pública y Alimentación" (SISPAL) [in English "Information System for Public Health and Food"] which includes information on previous vaccination history, including influenza, PPV23 and PCV13 vaccination, with lot number and date of administration per person.

Pneumococcal vaccination status will be based on whether receipt of ≥ 1 dose of PCV13 or PPV23 could be confirmed by electronic registries. All available vaccination data will be collected from the registry on subjects and time from vaccination will be incorporated in the analysis phase. Patients will be included regardless of the timing of their vaccination relative to their qualifying pneumonia admission but will be excluded from vaccine effectiveness

PFIZER CONFIDENTIAL CT45-GSOP-RF152.0 Low-Interventional Study Protocol Template 05-Dec-2019 Page 8 of 70

(VE) and serotype distribution analysis if they received pneumococcal vaccination \leq 30 days before hospitalisation for CAP because of risk of false positive UAD test. We will obtain previous influenza vaccination status (within the last year) via electronic registries as well.

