For the primary endpoint, the cases will be the patients with CAP in whom PCV13 serotypes are identified by any method and the controls will be the patients with CAP without having VT serotype (even the CAPs for which the serotype was not identified). Multivariable logistic regression model (Appendix 3.3), will be applied to estimate odds of exposure to PCV13 among cases versus controls. All VE estimates will be calculated as  $(1 - \text{odds ratio}) \times 100\%$ . Both unadjusted and adjusted VE will be estimated. Patients' age, sex, study site and the variables deemed to be potential confounders on the basis of prior knowledge (e.g. nationality to be modeled as Spanish vs. non-Spanish; risk level to be modeled as low vs. at-risk vs. high-risk; BMI category to be modeled as obese vs. overweight vs. normal vs. underweight; PSI score as continuous; current drug abuse; antibiotic use within past 14 days; influenza vaccination within the last year; pneumonia in last year [ordinal variable, 0,1,2,3] and PPV23 receipt in past 5 years) will be included in the multivariable regression model for adjustment. Initially, we will employ bivariate models, and only the variables significant at p<.20 in the bivariate models will be included in the final model for adjustment.

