## Variables to be used to calculate the propensity scores

Variables for calculating the propensity score.

- Patients' age: continuous
- Sex: female=0, male=1
- Nationality: Spanish=0, non-Spanish=1
- Risk level: low-risk=0, at-risk=1, high-risk=2
- PSI score: continuous
- Antibiotic use within past 14 days: no=0, yes=1)
- Influenza vaccination within past one year: yes=0, no=1
- Pneumonia in the last year: ordinal value=0, 1,2,3
- Season of admission: Spring (Mar-May)=0, Summer (Jun-Aug)=1, Autumn (sep-Nov)=2, Winter (Dec-Feb)=3.
- PPV23 receipt in past 5 years: yes=0, no=1
- CAP event occurrence during COVID-19 pandemic: 0=not during COVID-19, 1=During COVID-19 (The study is started in the pandemic period; the variable will be used if we find a non-pandemic period during the study period)

The study site will be exactly matched. Note that the categorical variable will be put in the model like the ordinal values.

The conditional logistic regression will be employed to estimate odds of exposure to PCV13 among these matched cases and controls. The VE estimate will be calculated as  $(1 - \text{odds ratio}) \times 100\%$ . We will use a two-sided alpha of 0.05 for all analyses.

In the 2nd sensitivity analysis (PPV23 Naïve population), the cases will be the hospitalized CAP in whom PCV13 serotypes are identified by any method and had not received PPV23 in the last five years from the date of visit; the controls (also PPV23 Naïve population), will be selected using the propensity score matching as described above. A conditional logistic regression will be employed to estimate odds of exposure to PCV13 among cases versus controls in the PPV23 naïve population. The VE estimate will be calculated as (1 – odds ratio) × 100%. We will use a two-sided alpha of 0.05 for all analyses.

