## 6.3.2.1. Exploratory Endpoint 2 - Main Analysis

In this analysis, the VE of PCV13 against VT (PCV13) pneumococcal CAP will be obtained from the primary analysis as described in Section 6.1.1.1. The same method will be used to estimate the VE of PPV23 against VT (PPV23) pneumococcal CAP. The crude difference will then be calculated as:

VE of PCV13 against VT (PCV13) pneumococcal CAP – VE of PPV23 against VT (PPV23) pneumococcal CAP

To evaluate the differences of the effectiveness of these two vaccines, the ORs from both the models that used conditional logistic regression using the propensity matching cases and controls, will be tested using the likelihood ratio and/or z-score test as described in Appendix 3.4.

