# **Appendix 2. Data Derivation Details**

# Appendix 2.1. Serotypes

Central laboratories will perform pneumococcal serotyping for all participants with *S. pneumoniae* (*Sp*) isolated by culture.

VT is defined as serotypes included in PCV20, PCV13, PCV7 or the PPV23

PCV7 serotypes: 4, 6B, 9V, 14, 18C, 19F and 23F.

DMB02-GSOP-RF02 5.0 Statistical Analysis Plan Template 05-Dec-2019
PFIZER CONFIDENTIAL
Page 47
TMF Doc ID: 98.03

PCV13 serotypes: 1, 3, 4, 5, 6A, 6B, 7F, 9V, 14, 18C, 19A, 19F, and 23F.

PCV20 serotypes: 1, 3, 4, 5, 6A, 6B, 7F, 8, 9V, 10A, 11A, 12F, 14, 15B, 18C, 19A, 19F, 22F, 23F, and 33F.

PPV23 serotypes: 1, 2, 3, 4, 5, 6B, 7F, 8, 9N, 9V, 10A, 11A, 12F, 14, 15B, 17F, 18C, 19F, 19A, 20, 22F, 23F and 33F.

[figure not shown]
NVT are serotypes that are not included in any of PCV20, PCV13, PCV7, or PPV23.

Non-typeable or Untypeable (UT) is defined as a result which could not be serotyped. This is a valid result and so will be summarized as a separate line. Note that this is not the same as a missing serotype result.

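### PCV13 receipt is not prespecified as a covariate in the PPV23 effectiveness models, leaving the exploratory PPV23 VE and the PCV13-minus-PPV23 difference open to confounding of unknown sign

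*SAP*

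**What the plan says.** SAP 6.3.2.1 takes PCV13 VE from the primary analysis and then states: "The same method will be used to estimate the VE of PPV23 against VT (PPV23) pneumococcal CAP". For the formal comparison it specifies that "the ORs from both the models that used conditional logistic regression using the propensity matching cases and controls, will be tested".

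Two covariate lists come with that method.

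- **Regression (SAP 6.1.1.1).** The adjustment set is age, sex, site and "the variables deemed to be potential confounders on the basis of prior knowledge (e.g. nationality to be modeled as Spanish vs. non-Spanish", followed by further examples and ending: "PPV23 receipt in past 5 years) will be included in the multivariable regression model for adjustment". No PCV13 item is named. A bivariate screen at p<.20 then decides what stays; Appendix 3.3 gives p<0.10.
- **Propensity score (SAP 6.1.1.2).** This list is itemised, with no wording that leaves it open. Its only pneumococcal-vaccine entry is "PPV23 receipt in past 5 years: yes=0, no=1".

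Protocol Section 3 describes how PCV13 is given to people aged 60 and over who have already had PPV23: those with underlying disease or at high risk receive it, and "others without risk factors will not receive another pneumococcal vaccination". Protocol Section 7 and Table 1 recommend PCV13 for adults over 60 who have had neither vaccine.

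For PCV13 VE, the plan includes a PPV23 covariate and a PPV23-naive sensitivity analysis (Protocol 12.1.3.2; SAP 6.1.1.2). No PCV13-naive counterpart is planned for PPV23 VE.

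**The concern.** The two sides of the comparison are treated differently. The PCV13 models name the other vaccine as a covariate; the PPV23 models, followed as written, do not.

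PCV13 receipt can confound PPV23 VE for two reasons. It lowers the risk of the shared serotypes, which count as PPV23 outcomes. It is also linked to PPV23 history by policy. That link operates inside the low-risk stratum, where prior PPV23 recipients are not offered PCV13 and unvaccinated people are, so adjusting for risk level does not remove it.

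What is at stake is the exploratory PPV23 VE and the difference between the vaccines, for which Protocol 12.4.1 sets a null hypothesis of no difference. The SAP 6.1.1.1 exclusions do not close the gap: they remove people with discordant PCV13-after-PPV23 intervals and PCV20 recipients, not PCV13 exposure in general.

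**Working it through.** **The plan's own figure.** The only sizing figure is for PCV13: 170 cases and 1,692 controls (SAP 2.2). With 15% coverage in controls and VE 60%, exposure in cases is 0.4×0.15 / (0.85 + 0.4×0.15) = 0.0659. The Fleiss formula with continuity correction, two-sided alpha 0.025, 80% power and a ratio of 1692/170 gives 170 cases, as stated. This point does not change it. No sizing is given for PPV23 VE or for the difference.

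**Serotype overlap (SAP Appendix 2.1).** PCV13: "PCV13 serotypes: 1, 3, 4, 5, 6A, 6B, 7F, 9V, 14, 18C, 19A, 19F, and 23F". PPV23: "1, 2, 3, 4, 5, 6B, 7F, 8, 9N, 9V, 10A, 11A, 12F, 14, 15B, 17F, 18C, 19F, 19A, 20, 22F, 23F and 33F". Twelve types are in both; only 6A is in PCV13 alone.

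**Effect of leaving PCV13 out.** Let s be the share of PPV23-type cases due to the 12 shared types in people without PCV13. Let c1 and c0 be PCV13 coverage in controls with and without PPV23. With multiplicative effects and PPV23 VE equal across its types:

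observed OR = (1 − VE of PPV23) × (1 − VE13·s·c1) / (1 − VE13·s·c0)

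Inputs:
- PCV13 VE 60% and PCV13 coverage 15%: the documents' planning values.
- PPV23 coverage 45%: assumed, close to the 46.7% cohort-weighted average from Protocol Table 2 for ages 60 to 75.
- s from 30% to 90%: assumed.
- PCV13-PPV23 association odds ratio from 0.1 to 4: assumed.
- True PPV23 VE 30%: assumed.

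Observed PPV23 VE (%) when the true value is 30%:

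| Association OR | c0 / c1 (%) | s=30% | s=50% | s=70% | s=90% |
|---|---|---|---|---|---|
| 0.1 | 24.7 / 3.2 | 27.2 | 25.1 | 22.9 | 20.6 |
| 0.25 | 21.9 / 6.6 | 28.0 | 26.5 | 25.0 | 23.4 |
| 0.5 | 18.8 / 10.4 | 28.9 | 28.1 | 27.3 | 26.5 |
| 1 | 15 / 15 | 30.0 | 30.0 | 30.0 | 30.0 |
| 2 | 11.0 / 19.9 | 31.1 | 31.9 | 32.7 | 33.6 |
| 4 | 7.4 / 24.3 | 32.2 | 33.6 | 35.1 | 36.6 |

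One corner in full: with s=0.9 and OR 0.1, the factor is (1 − 0.6×0.9×0.032) / (1 − 0.6×0.9×0.247) = 0.983/0.867 = 1.134, and 1 − 0.70×1.134 = 20.6%.

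If PCV13 VE is itself estimated as 60%, the true 30-point difference would read between 60 − 20.6 = 39.4 and 60 − 36.6 = 23.4 points.

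**Where s may lie.** Protocol Section 7 gives invasive-disease rates at age 60 and over in 2013-2015: PCV7 types 1.25, other PCV13 types 3.45, total 17.09 per 100,000. PCV13 types are therefore (1.25 + 3.45)/17.09 = 27.5%. Types 8 and 22F, which are in PPV23 only, are put at 25%. That caps s near 27.5/(27.5 + 25) = 52%. If the 25% refers only to non-PCV13 disease, the cap is 27.5/(27.5 + 0.25×72.5) = 60%. These are invasive-disease figures, not CAP, but they favour the left half of the table.

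**Where the association may lie.** At age 75, Table 2 has 15.70% with PCV13 and 94.90% with PPV23, so at least 15.70 + 94.90 − 100 = 10.6% have had both. Joint use is common, but this minimum does not settle the sign.

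**The case against.** The strongest reply is that the SAP does not exclude PCV13 from the PPV23 regression. That list is introduced by examples and was written with PCV13 as the exposure. Taken literally for PPV23, it would adjust PPV23 exposure for part of itself, so some transposition is clearly intended, and substituting the other vaccine is the natural one. SAP 6.5.3 also plans a PCV13-by-PPV23 overlap table. For the regression this stands: the supportable statement is that PCV13 is not prespecified. It does not rescue the propensity score, whose list is itemised and feeds the formal test.

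A reader might infer that PPV23 VE is biased downwards and the comparison tilted towards PCV13. The documents do not support a fixed direction. Giving PCV13 to PPV23-naive adults pushes that way. But Table 1 also provides both vaccines for high-risk adults, PCV13 after PPV23 for those with underlying disease, and both vaccines for the 1956-57 cohorts before 2018; these push the other way.

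The shift is also modest against sampling error. Assuming 300 to 650 PPV23-type cases with eight controls each, an unadjusted 95% interval around 30% runs from about 10-45% to about 17-41%. That stands, although a bias does not shrink as cases accrue.

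Finally, PCV13 given after PPV23 is partly a consequence of PPV23 history, so conditioning on it is a choice of estimand. That is fair, and the SAP should state the choice.

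**Conclusion.** The point holds as a gap in prespecification for an exploratory endpoint. Followed as written, the propensity-matched PPV23 model omits a vaccine that acts on 12 of its 23 outcome types and whose use depends on PPV23 history; the regression leaves the matter open.

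Under the inputs above, a true PPV23 VE of 30% would read from about 21% to about 37%, and the difference would move by the opposite amount. With s at 50% or below, nearer the protocol's invasive-disease figures, the range is about 25% to 34%. There is no bias if the two vaccines are unassociated. The range is illustrative, not a bound: it rests on an assumed association and shared-type fraction, and takes no account of risk strata.

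The primary PCV13 VE is not affected, since its models name a PPV23 term. This is a cheap improvement.

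**What to change.** In SAP 6.3.2.1, state that for every PPV23 VE model:

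- PCV13 receipt before admission, with the same definition and look-back as the PCV13 exposure in SAP 6.1.1.1, replaces the recent-PPV23 item in both the propensity score and the regression.
- This term is kept regardless of the bivariate screen.
- The estimand is PPV23 VE with PCV13 status held fixed.

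Add a PCV13-naive sensitivity analysis for PPV23 VE, mirroring the PPV23-naive analysis planned for PCV13.

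The cost is SAP wording; PCV13 dates are already collected from the vaccination registry. The statistical price is a slightly wider PPV23 interval where the two vaccines are correlated.

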# 6.3.3. Exploratory Endpoint 3 – Compare serotype results for carriage testing by specimen type

Percent agreement in serotype results for each serotype among the CAP population who have at least two of the three following specimen results available: a) high-quality respiratory specimen (SOC), b) UAD1/2 (study procedure), and c) saliva.

## 6.3.3.1. Exploratory Endpoint 3 - Main Analysis

The percentages of specimens with serotype results (for each serotype) by method of detection will be determined dividing the number of specified serotypes identified by the total number of specimens tested by the detection method.

DMB02-GSOP-RF02 5.0 Statistical Analysis Plan Template 05-Dec-2019
PFIZER CONFIDENTIAL
Page 37
TMF Doc ID: 98.03

Cohen's kappa will be used to describe the agreement between the detection methods. Each comparison will involve two specimen types only (i.e, UAD versus saliva, UAD versus respiratory culture, Saliva versus respiratory culture). The kappa term ranges from -1 to 1. If the agreement is less than what would be expected by chance than it will be negative. The following labels are assigned to the corresponding ranges of kappa strength: <0 is poor agreement, 0.00-0.20 is considered slight agreement, 0.21-0.40 is fair agreement, 0.41-0.60 is moderate agreement, substantial 0.61-0.80 is substantial agreement, and 0.81-1.00 is perfect agreement.

Besides the kappa statistic, concordant and discordant pairs will be counted among these three methods, and the McNemar's test, a nonparametric method, will be used to assess the level of imbalance in the discordant status between specified serotype identified in each of these tests.

A venn diagram will be produced to represent the concordant and discordant pairs among these three methods.

# 6.3.4. Exploratory Endpoint 4 - Incidence Rate of CAP cases with specific risk condition

The incidence rate of CAP residents with a specific risk conditions will be calculated using the number of CAP events, identified in the screening log, multiplied by the proportion of CAP population with specific risk condition(s), divided by the estimated number of persons ≥60 years in surveillance region with the same specific risk condition(s), in aggregate for at-risk and high-risk conditions and for individual risk groups.

# 6.3.4.1. Exploratory Endpoint 4 - Main Analysis

The incidence rate among the high-risk population  $(IR_{hr})$  will be calculated as

$$IR_{hr} = \frac{(\textit{no.of cases in the high risk category} \div \textit{no.of years of surveillance})}{\textit{total high risk population in the hospitals' geographical catchment area}} \times 100,000$$

The incidence rate among the at-risk population  $(IR_{ar})$  will be calculated as

$$IR_{ar} = \frac{(no.\,of\,\,cases\,\,in\,\,the\,\,at\,\,risk\,\,category\,\div\,no.\,of\,\,years\,\,of\,\,surveillance)}{total\,\,at\,\,risk\,\,population\,\,in\,\,the\,\,hospitals'\,geographical\,\,catchment\,\,\,area} \times 100,000$$

The no. of years of surveillance will be calculated as

(date of last participant first visit – date of the start of surveillance period +1)/365.25

If the data do not provide complete years (e.g. 1 year, 2 years, etc.), then the no. of years of surveillance will be adjusted for seasonality, if the data on seasonality are available for the sites.

Note that we will apply the proportion of CAP events in a specific risk group among enrolled participants to account for the number of CAP events in specific risk group among the unenrolled patients. The risk population will be obtained by multiplying the frequency of a given risk factor obtained from other sources (e.g., UAD control subjects or real-world data analyses) by

DMB02-GSOP-RF02 5.0 Statistical Analysis Plan Template 05-Dec-2019
PFIZER CONFIDENTIAL
Page 38
TMF Doc ID: 98.03

denominator counts for that age group from local government sources. This analysis will be performed if such data are made available.

# 6.3.5. COVID-19 Related Endpoint 1 – Distribution of the CAP cases by COVID-19 positive and negative

Percentage of CAP cases with pneumococcal infection identified by any means (UAD, BinaxNOW, or bacterial culture) associated with a positive COVID-19 test compared to percentage of CAP cases with pneumococcal infection identified by any means (e.g., UAD, BinaxNOW, bacterial culture) associated with a negative COVID-19 test, overall and stratified by age, sex, and pneumococcal risk status.

# 6.3.5.1. COVID-19 Related Endpoint 1 - Main Analysis

The following calculations will be made for overall and stratified by age group, sex, and pneumococcal risk status among COVID-19 subpopulations (test positive or negative), i.e., all enrolled population with a valid results from COVID-19 viral testing. The following calculations will be made:

- Proportion (95% CI for proportion) of CAP events with pneumococcus among COVID-19 test positive cases
- Proportion (95% CI for proportion) of CAP events with pneumococcus among COVID-19 test negative cases

These will also be calculated for the following subgroups: age group (60-74 years, 75-84 years and ≥85 years), sex, and pneumococcal risk status.

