5. MILESTONES

Milestone	Planned date
Completion of feasibility assessment	Q2 2020
Start of data collection (FSFV)	March 2021
End of data collection (LSLV)	Q1 2025
Interim Analysis	After approximately 170 immunocompetent VT-CAP
Study results	Q2 2025
Final study report	Q3 2025

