An interim analysis is planned after accrual of 170 VT-cases but depending on the VE point estimate, the proportion of CAP cases that are vaccine serotype, and the frequency of PCV-13 vaccination in the study population, additional subjects may be needed to allow for adequate statistical power. On this basis, approximately 4 years of enrolment is planned.

If the anticipated PCV20 is approved during the enrolment of cases for VE analysis as expected (projected to be in use no sooner than late 2022), subjects with PCV20 exposure will be excluded from the cases and the controls for the PCV13 VE analysis. Initial PVC20 use is expected to primarily involve those aging into the over 60 age group, and substantial number of persons with a history of PCV13 vaccination are expected to remain in that age group population.

Laboratory testing. The Central laboratory will conduct BinaxNOW[®] (Alere, Walthman, MA) and the serotype-specific UAD1 and 2 assays (Pfizer, Inc) to test urine samples from all enrolled participants as the study-related procedures. Results from SOC tests performed on enrolled subjects will be also collected, including respiratory, blood, and pleural fluid cultures and urine pneumococcal antigen testing. All pneumococcal isolates will undergo serotyping.

Pneumococcal Carriage and RSV infection assessments. In addition, patients at selected study sites will provide a saliva sample to test for pneumococcal carriage and RSV infection but, if they decline this procedure at the time of collection, they will not be excluded from the study. Samples will be processed for pneumococcal detection by the standard, conventional culture diagnostic approach and molecular methods. RSV will be detected by molecular methods only.

Incidence assessment. Population-based incidence of CAP will also be estimated in this study. Nearly all CAP hospitalisations in the surveillance regions are expected to involve the study hospitals. Every effort will be taken to identify all pneumonia patients admitted to

PFIZER CONFIDENTIAL CT45-GSOP-RF152.0 Low-Interventional Study Protocol Template 05-Dec-2019 Page 30 of 70

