study hospitals. Patients with pneumonia who are not enrolled will be recorded on the screening log, which will be the basis of the count of CAP events for incidence estimates. Where appropriate population-based denominators are available, incidence rates for at-risk and high-risk conditions will be generated in aggregate and by condition for more frequent conditions. Nevertheless, incidence estimates will be conservative, given established multiple risks for under ascertainment of pneumonia events in studies in this setting (for example, due to misdiagnosis, chest X-ray [CXR] false negative, or hospitalisation on a different inpatient ward). Non-residents of the hospitals' geographic catchment area will be excluded from incidence estimations.

COVID-19 and pneumococcal infection. The World Health Organization declared COVID-19 a pandemic during the finalization of this protocol (March 11, 2020). On this basis, additional exploratory objectives related to the relationship between COVID-19 and pneumococcal infection were added. If COVID-19 continues to occur at a sufficient frequency in the surveillance region during enrolment to allow for a meaningful analysis, these objectives will be pursued using COVID-19 infection status based on standard –of care testing. Further, if a high incidence of COVID-19 infections is burdening the hospitals at the anticipated time of study start or at some point during study enrolment period, enrolment will be delayed or halted to allow involved staff to focus on COVID-19 clinical care.

This study will prospectively enroll adults, aged 60 years and over, who are hospitalised with CAP in one of the study hospitals: Hospital Universitario de Móstoles, Hospital Universitario Fundación de Alcorcón, and Hospital Rey Juan Carlos de Móstoles (as of February 2022, additional sites may be included at a later date).

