#### Results of the Respiratory Specimens for Viral Testing

DMB02-GSOP-RF02 5.0 Statistical Analysis Plan Template 05-Dec-2019
PFIZER CONFIDENTIAL
Page 22
TMF Doc ID: 98.03

Results of SOC testing for viral pathogens in respiratory specimens collected upon admission will be documented in the CRF. This includes documentation of COVID-19 results when available. SOC viral testing results via PCR and/or viral culture will also be documented. For RSV and COVID-19, both negative and positive test results will be documented.

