## 5.3. Methods to Manage Missing Data

Analyses will be based on all available data. Participants who have data missing for a certain analysis will be excluded only from that analysis. For example, if a participants has missing UAD assay results but has results available from Binax and culture, then the participants will be excluded from any analyses requiring the UAD results, but will be included in any analyses requiring results from Binax or culture.

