#### 6.3.6.1. COVID-19 Related Endpoint 2 - Main Analysis

The patients with COVID-19 will be divided into two groups:

- those with coinfection with Sp identified by any means (e.g., UAD, Binax, bacterial culture)
- Those without coinfection with Sp identified by any means (e.g., UAD, Binax, bacterial culture)

The severe clinical outcomes are:

- Admitted to ICU (yes vs. no)
- PaO2/FiO2 ratio <250 mmHg (yes vs. no)

DMB02-GSOP-RF02 5.0 Statistical Analysis Plan Template 05-Dec-2019
PFIZER CONFIDENTIAL
Page 39
TMF Doc ID: 98.03

- Respiratory rate >30 breaths/min (yes vs. no)
- Died (yes vs. no)
- Received mechanical ventilation (yes vs. no)
- Diagnosed as ARDS (yes vs. no)
- Any one of the above (yes. vs. no)

The difference in the severe clinical outcomes between the two groups will be evaluated using Chi-square or Fisher's Exact test, as appropriate.

The analysis will also be done stratifying by age group (60-74 years,75-84 years and ≥85 years), sex, and pneumococcal risk status.

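### COVID-19 Endpoints 1 and 4 pool over more than three years and a changing set of hospitals with no term for period or site, so the crude comparison can show an association that no single period contains

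*SAP*

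**What the plan says.** **Endpoint 1 (SAP 6.3.5.1).** "The following calculations will be made for overall and stratified by age group, sex, and pneumococcal risk status among COVID-19 subpopulations". The output is a pair of percentages, the first being "Proportion (95% CI for proportion) of CAP events with pneumococcus among COVID-19 test positive cases" and the second its counterpart in COVID-19 negatives.

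**Endpoint 4 (SAP 6.3.8, 6.3.8.1).** Carriage is compared between patients with and without COVID-19 by chi-square or Fisher's exact test, with the same three breakdowns.

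**Endpoint 2 (SAP 6.3.6.1).** Within COVID-19 positive patients, severe outcomes are compared by pneumococcal co-infection. "The analysis will also be done stratifying by age group", sex and risk status.

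**Endpoint 3 (SAP 6.3.7.1).** This one differs. It uses the propensity-score matching of SAP 6.1.1.2, which includes season of admission, a pandemic-period indicator if a non-pandemic period occurs, and exact matching on site.

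**COVID-19 status.** Under Protocol 9.1, "these objectives will be pursued using COVID-19 infection status based on standard –of care testing". SAP 3.4 adds: "This includes documentation of COVID-19 results when available". For patients without a result, SAP 5.3 applies: "Participants who have data missing for a certain analysis will be excluded only from that analysis".

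**Time and sites.** Protocol section 5 gives "Start of data collection (FSFV) March 2021" and a last subject last visit in Q1 2025. Protocol 9.1 records the third hospital as joining in February 2022 and allows enrolment to be delayed or halted when the COVID-19 burden is high.

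**The concern.** The protocol asks whether the frequency of pneumococcal infection, and of carriage, differs by COVID-19 status. Over an enrolment of this length, the proportion of pneumonia patients with COVID-19, the readiness to test for it, the mix of hospitals and the circulation of pneumococcus could all change. When two of these move together, patients with and without COVID-19 come from different mixtures of periods and sites. The pooled percentages then partly compare periods, not COVID-19 status.

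Breakdowns by age, sex and risk do not remove this, because each subgroup is itself pooled over the whole period. The SAP already treats season, pandemic period and site as potential confounders in its propensity-score matching, but does not carry them over to Endpoints 1, 2 and 4. At stake is the reading of an exploratory result: a shift over time could be taken for an effect of COVID-19 on pneumococcal infection, or the reverse.

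**Working it through.** **Plan figures.** The documents state no sample size, power or error rate for any COVID-19 comparison, so there is no figure to reproduce. The 170 cases in SAP 2.2 belong to the primary vaccine-effectiveness analysis.

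**Length of enrolment.** The last visit is 180 to 195 days after admission.
- Longest: 1 March 2021 to 31 March 2025 is 4.08 years; less 180 days (0.49) = 3.59 years.
- Shortest: 31 March 2021 to 1 January 2025 is 3.76 years; less 195 days (0.53) = 3.22 years.

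**Model.** Let period k have weight w, COVID-19 share c and pneumococcal share s, with no association inside any period. Then:
- P(Sp+ | COVID+) = Σwcs / Σwc
- P(Sp+ | COVID−) = Σw(1−c)s / Σw(1−c)
- Difference = Cov(c, s) / [c̄(1−c̄)]

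The last line gives the condition: the crude difference is zero unless c and s vary together across periods. The same algebra holds with sites in place of periods.

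**Worked example (assumed shares, four equal years).** c = 50/30/15/10% and s = 10/14/18/18%.
- COVID+: (0.050 + 0.042 + 0.027 + 0.018) / 1.05 = 0.137 / 1.05 = 13.0%
- COVID−: (0.050 + 0.098 + 0.153 + 0.162) / 2.95 = 0.463 / 2.95 = 15.7%
- Pooled OR = (0.137 × 2.487) / (0.913 × 0.463) = 0.81

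**Range.** Each row was also simulated 4,000 times per sample size. N = 2,000 is the lower end of planned enrolment. N = 5,040 is 1,800 × 0.70 × 4, from the protocol's admissions, participation and duration. Rejection is by a nominal two-sided 5% chi-square test; the true OR is 1.0 in every row.

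| Drift | COVID-19 share by year, % | Sp+ share by year, % | Sp+ in COVID+ vs COVID− | Pooled OR | Rejects, N=2,000 | Rejects, N=5,040 |
|---|---|---|---|---|---|---|
| Mild opposite | 30/25/15/10 | 13/14/16/17 | 14.4% vs 15.2% | 0.94 | 7% | 9% |
| Moderate opposite | 50/30/15/10 | 10/14/18/18 | 13.0% vs 15.7% | 0.81 | 31% | 66% |
| Strong opposite | 60/30/10/5 | 8/14/20/22 | 11.5% vs 17.6% | 0.61 | 92% | >99% |
| Same direction | 50/30/15/10 | 18/16/14/12 | 16.3% vs 14.5% | 1.14 | 17% | 33% |
| COVID-19 share only | 40/25/10/10 | 15 throughout | 15.0% vs 15.0% | 1.00 | 5% | 5% |
| Sp+ share only | 20 throughout | 10/14/18/18 | 15.0% vs 15.0% | 1.00 | 5% | 4% |

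Stratifying by year with the Mantel-Haenszel estimator, Σ(ad/n) / Σ(bc/n), gives an OR of 0.99 to 1.00 and rejection of 4% to 6% in every row.

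The range is illustrative, not a bound. Take 12 early and 30 later months, COVID-19 share 60% then 10%, and Sp+ 5% then 20%. COVID+ is (0.36 + 0.60) / 10.2 = 9.4%, COVID− is (0.24 + 5.40) / 31.8 = 17.7%, and the OR is 0.48.

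**Limits of the check.** Both sample sizes treat every patient as tested for COVID-19, and four full years exceed the enrolment window found above, so the rejection rates are towards the high side. The Sp+ shares stand for infection; carriage shares would differ. No calculation is offered for Endpoint 2.

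**The case against.** Several points on the other side stand.

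- A reader might infer that pooling creates an association by construction. It does not. Both shares must vary over the same periods or sites. The documents give neither, so the size and even the direction of any bias are unknown. The option to halt enrolment under COVID-19 pressure could also remove many surge patients.
- A reader might extend the point to all the COVID-19 comparisons. Endpoint 3 already has season, site and a conditional pandemic term. Endpoint 2 lies within COVID-19 positives and so cannot produce a COVID-pneumococcus association. It can still be confounded if severity and co-infection both change over time.
- Pneumococcal detection is largely protected from selective testing: Protocol 9.1 plans central BinaxNOW and UAD "to test urine samples from all enrolled participants as the study-related procedures". On the COVID-19 side, negative as well as positive results are recorded, and later results can be added at Visit 2. Selective COVID-19 testing is possible, but the documents do not show it.
- These analyses are exploratory and run only if COVID-19 is frequent enough. SAP 5.1 disclaims hypothesis tests, and SAP 6.3.5.1 names none for Endpoint 1, so the rejection rates describe an informal comparison there. This carries less weight than it seems: SAP 6.3.8.1 names chi-square or Fisher for Endpoint 4, Protocol 12.4.1 names such tests for the other objectives generally, and the objective is worded as a difference.
- Fine strata would be sparse. Two sites for 4 quarters and three for 10 make 8 + 30 = 38 cells. With 4,000 patients spread evenly over 42 months, a late COVID-19 share of 10% gives about 286 positives in 30 cells, or 9 to 10 each, with about 2 Sp+ at 20%. Coarser periods are needed.

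**Conclusion.** The point holds for Endpoints 1 and 4 as a risk of confounding by period and site, not as a demonstrated bias. With assumed yearly shares and no association within any year, the pooled odds ratio runs from about 0.6 to 1.14, is near 0.94 under mild drift, and is exactly 1.00 when only one share drifts. All of these sizes rest on assumed shares, because the documents supply none. Endpoint 2 is exposed to a lesser degree, not quantified here. Endpoint 3 is not part of the point, and the primary vaccine-effectiveness analysis is unaffected.

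The change is worth making because the objective is comparative, the SAP already names the relevant variables elsewhere, and adjustment by period removes the artefact in every scenario examined.

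**What to change.** 1. In SAP 6.3.5.1 and 6.3.8.1, add a Mantel-Haenszel or logistic estimate of the association between COVID-19 and pneumococcal infection (or carriage, yes/no), adjusted for calendar period of admission, for example season-year or half-year, and for study site. Base the interpretation on this estimate and keep the pooled percentages as descriptive.
2. In SAP 6.3.6.1, add the same adjustment as a supportive analysis where counts allow, with coarse periods: year, or the season and pandemic terms already defined in SAP 6.1.1.2.
3. Tabulate the share of CAP patients with a valid COVID-19 result by period and site, so that readers can judge who entered the comparison.

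Cost: SAP wording and a few tables. Admission date and site are already collected (Protocol 10.2 and 10.3). Intervals will be somewhat wider and some strata will carry no information, chiefly for Endpoint 2 and for carriage, where the protocol takes saliva only at selected sites.
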